2.2 Study Design

2.2.1 Overview

This study is a placebo-controlled, double-blind, randomized, Phase 3 study to evaluate the efficacy, safety, and tolerability of obicetrapib 10 mg, both as an FDC with ezetimibe 10 mg and as monotherapy, on top of maximally tolerated lipid-modifying therapy. This study will take place at approximately 60 sites.

Screening Period

At Screening (Visit 1), participants will be required to sign an informed consent form (ICF) before any study-related procedures are performed. After signing the ICF, participants will be assessed for study eligibility.

Treatment Period

Up to 2 weeks after Screening (Visit 1), participants will return to the site on Visit 2 (Day 1) and confirm study eligibility before being randomized and beginning treatment. Approximately 400 eligible participants (100 participants per treatment group) will be randomized in a 1:1:1:1 ratio to 1 of the following treatment groups:

- FDC therapy: Obicetrapib 10 mg + ezetimibe 10 mg;
- Obicetrapib monotherapy: Obicetrapib 10 mg;

- Ezetimibe monotherapy: Ezetimibe 10 mg; or
- Placebo.

Approximately 70% of the participants enrolled into this study should be taking high intensity statins (HIS). No more than approximately 10% of participants in this study will be completely statin intolerant.

Participants without underlying HeFH or a history of ASCVD but with multiple ASCVD risk factors will comprise a maximum of 30% of the total participants enrolled into the study. Participants with only HeFH will comprise a maximum of 20% of the total participants enrolled into the study.

During the 12-week Treatment Period, the assigned study drugs will be administered by the participants orally with water, with or without food, once daily on Day 1 to Day 84 at approximately the same time each morning. Participants will return to the site on Visit 3 (Day 28) (\pm 7 days) and Visit 4 (Day 84) (\pm 7 days) for efficacy and safety assessments. Participants, Investigators, the Clinical Research Organization, and the Sponsor will be blinded to all lipid results from Day 1 (Visit 2) for the first participant until the database is locked in order to protect blinding to treatment assignment.

Safety Follow-Up Period

Participants will return to the site for a Safety Follow-up Visit (Visit 5 [Day 112]) approximately 4 weeks after the end of the Treatment Period for safety assessments.

Refer to Table 1 Schedule of Procedures for a complete list of procedures to be completed at each study visit.

2.2.2 Sample Size Determination

A sample size of at least 380 evaluable participants (ie, 95 participants per treatment group) will provide more than 90% power to detect a 30% difference in LDL-C reduction at Day 84 (SD of 25%) for the obicetrapib 10 mg + ezetimibe 10 mg FDC treatment group compared with the placebo group at a 1-sided significance level of 0.025.

The sample size for this study was determined in order to provide sufficient power (>90%) for the analyses of the co-primary endpoints described above. A sample size of at least 380 evaluable participants (ie, 95 participants per treatment group) will provide more than 90% power to detect a 20% difference in LDL-C reduction at Day 84 for the obicetrapib 10 mg + ezetimibe 10 mg FDC treatment group compared with the ezetimibe 10 mg monotherapy treatment group, and it will provide more than 90% power to detect a 12% difference in LDL-C reduction at Day 84 for the obicetrapib 10 mg + ezetimibe 10 mg FDC treatment group compared with the obicetrapib 10 mg monotherapy treatment group, assuming an SD of 25% at a 1-sided significance level of 0.025.

In addition, the sample of 95 participants in the obicetrapib 10 mg monotherapy treatment group will provide more than 90% power to detect a 15% difference in LDL-C reduction at Day 84 compared with the placebo treatment group.

Therefore, assuming an approximately 5% dropout rate, enrollment of approximately 400 participants (ie, 100 participants per treatment group) is planned for this study. This sample size will also contribute sufficient participant exposure and safety data.

Table 1 Schedule of Procedures

	Screening ^{a,b} Treatment Period Sa		Safety Follow-Up			
Visit	1	2	3	4	5	
Week	Up to -2	0	4	12	16	EOT ^c
Day (±Visit Window)	-14 to -1	1	28 (±7)	84 (±7)	112 (±7)	_
Informed consent ^d	X					
Inclusion/exclusion criteria	X	Xe				
Demographic information	X					
Medical/surgical history	X					
Prior/concomitant medications	X	X	X	X	X	X
Weight and height ^f	X					
Physical examination ^g	X			X		X
Vital signs ^h	X	X	X	X	X	X
12-lead ECG ⁱ	X					
Urine pregnancy test ^j	X			X		X
FSH test ^k	X					
Fasting chemistry and hematology ¹	X	X	X	X	X	X
Coagulation parameters	X			X		X
Fasting lipid profile ^m	X	X	X	X		X
Fasting Lp(a) ⁿ		X		X		X
Urine sample for UACR	X	X	X	X	X	X
Pharmacokinetics ^o		X	X	X		X
Serum archive sample ^p		X		Xq		X
Randomization		X				
Dispense study drugs ^r		X	X			
Study drug administration ^s						
Study drug compliance			X	X^q		X
Register visit in IRT	X	X	X	X		X
Adverse events		X	X	X	X	X

Note: When several assessments are required at the same visit, samples for clinical laboratory assessments should be collected after completing other assessments, such as physical examinations, vital signs, and 12-lead ECGs.

Note: In cases of COVID-19 limitations, it is the Investigator's responsibility to assure the safety of participants. If necessary, the Sponsor will implement and document mitigation strategies as described in section 3.1.4 of the protocol. In the absence of a COVID-19 impact, it is expected that Investigators and participants follow the protocol requirements as set forth.

Note: For the purposes of this study, fasting will be defined as nothing by mouth except water and any essential medications for a minimum of 8 hours.

Note: Unscheduled visits may be scheduled as needed per the judgment of the Investigator. Procedures will be determined based on the reason for the visit.

- a. If laboratory abnormalities during the Screening Period are considered by the Investigator to be transient, then the laboratory tests may be repeated once during the Screening Period. The Investigator's rationale for retesting should be documented. If the retest result is no longer exclusionary, the participant may be randomized.
- b. A participant who is screened and does not meet the study eligibility criteria may be considered for rescreening upon Sponsor and/or Medical Monitor consultation and approval. Rescreened participants will be assigned a new participant number. Rescreening should occur no less than 5 days after the last screening visit.
- c. Participants who discontinue study drug between Visit 2 (Day 1) and Visit 3 (Day 28) or at Visit 3 (Day 28) should complete an EOT Visit at Day 28, return to complete Visit 4 (Day 84), and return to complete the Safety Follow-up Visit (Day 112). In addition, participants who withdraw from the study should complete an EOT Visit. Participants who discontinue study drug between Visit 3 (Day 28) and Visit 4 (Day 84) will not undergo an EOT Visit but continue with study visits per protocol.
- d. Participants will be required to sign an ICF before any study-related procedures are performed.
- e. Confirm the participant continues to meet the inclusion and exclusion criteria and assess any updates since Screening (Visit 1).
- f. Weight and height will be measured at Screening (Visit 1) and will be used to calculate body mass index. Measurement of weight should be performed with the participant dressed in indoor clothing, with shoes removed.
- g. The physical examination should comprise a focused examination, which includes general, respiratory, CV, abdominal, and extremities evaluations.
- h. Vital signs will include body temperature, heart rate, and triplicate blood pressure (systolic and diastolic) measurements. Participants should be in the supine position after at least 10 minutes rest prior to the vital sign measurements.
- i. A single 12-lead ECG will be performed in the supine position after 10 minutes of rest. ECGs are to be assessed for clinical significance by a qualified medical designee at the study site.
- j. For women of childbearing potential only.
- k. FSH test will be performed in women <55 years of age for whom it has been ≥1 year since their last menstrual period.
- 1. At Screening (Visit 1), Visit 4 (Day 84), and EOT, chemistry panel will include HbA1c.
- m. LDL-C, and VLDL-C will also be evaluated by NMR analysis for particle numbers and size. LDL-C level will be calculated using the Martin-Hopkins and Friedewald equations unless TG ≥400 mg/dL (≥4.5 mmol/L) or LDL-C ≤50 mg/dL (≤1.3 mmol/L); in both cases, LDL-C level will be measured directly by preparative ultracentrifugation, also referred to as beta quantification. Additionally, LDL-C will be measured by preparative ultracentrifugation at Visit 2 (Day 1), Visit 4 (Day 84), and EOT for all participants (Sources: Martin SS, Blaha MJ, Elshazly MB, et al. LDL calculator. Johns Hopkins Medicine. https://ldlcalculator.com. Accessed 27 October 2023; Friedewald W. LDL calculated. MDCalc. https://www.mdcalc.com/ldl-calculated. Accessed 11 November 2022).
- n. Samples should be collected prior to study drug administration.
- o. A PK sample will be collected prior to study drug administration for trough measurements of objectrapib and ezetimibe in plasma.
- p. Serum archive samples will be collected prior to the first dose at Visit 2 (Day 1) and at Visit 4 (Day 84) (or at an EOT Visit, in cases of early discontinuation) for potential future assessment of conditions associated with cholesterol metabolism. Samples should be collected prior to study drug administration and while the participant is fasting (a minimum of 8 hours). If the samples are analyzed, it will be for non-genetic tests.
- q. This assessment does not need to be repeated if the participant discontinued study drug early and has already undergone an EOT Visit.
- r. At Visit 2 (Day 1), participants will receive 1 kit (containing 36 FDC tablets or matching placebo tablets, 36 obicetrapib tablets or matching placebo tablets, and 36 ezetimibe capsules or matching placebo capsules totaling 108 tablets/capsules per kit) with the study drugs appropriate for the participant's treatment group. At Visit 3 (Day 28), participants will receive 2 kits as described above. The 2 kits provide sufficient supplies for 56 days of dosing, with enough for an extra 16 days of dosing in case the participant needs to postpone Visit 4 (Day 84). Each individual kit will provide a sufficient supply for 28 days of dosing, with enough for an extra 8 days of dosing. Participants will be instructed to take 3 units from the kit each day. The kit will be clearly labelled to indicate which tablets and capsule to use on each day. Participants will be instructed to bring all unused study drugs to the site at the next visit.
- s. Study drugs (2 tablets and 1 capsule) will be administered by the participant orally with water, with or without food, once daily on Day 1 to Day 84 at approximately the same time each morning. On days with visits scheduled, participants should not take the study drugs prior to the visit but should bring the study drugs with them to the site. The study drugs will be administered with water following all fasted blood samples. At Visits 3 and 4, participants will dose from the kit received at the previous visit (Visits 2 and 3, respectively). If a participant permanently discontinues study drug, he/she will continue to participate in study visits, as described in section 4.5 of the protocol, but will no longer administer study drug.

COVID-19 = Coronavirus Disease 2019; CV = cardiovascular; ECG = electrocardiogram; EOT = End of Treatment; FDC = fixed dose combination; FSH = follicle-stimulating hormone; HbA1c = glycosylated hemoglobin; HDL-C = high-density lipoprotein cholesterol; ICF = informed consent form; IRT = interactive response technology; LDL-C = low-density lipoprotein cholesterol; Lp(a) = lipoprotein (a); NMR = nuclear magnetic resonance; PK = pharmacokinetic(s); TG = triglyceride(s); UACR = urine albumin-creatinine ratio; VLDL-C = very low-density lipoprotein cholesterol.

2.3 Study Endpoints

2.3.1 Primary Efficacy Endpoints

The primary efficacy endpoint is the percent change from Day 1 to Day 84 in LDL-C. Co-primary endpoints include the percent change from Day 1 to Day 84 in LDL-C for the obicetrapib 10 mg + ezetimibe 10 mg FDC treatment group as follows:

- Compared with the placebo group;
- Compared with the ezetimibe 10 mg monotherapy treatment group; and
- Compared with the obicetrapib 10 mg monotherapy treatment group.

And the percent change from Day 1 to Day 84 in LDL-C for the obicetrapib 10 mg monotherapy treatment group compared with the placebo group.

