 - For any participant not taking statin therapy due to statin intolerance, including those participants taking bempedoic acid or fibrate monotherapy, written confirmation will be required of both the participant and the Investigator stating that the participant is statin intolerant, aware of the benefit of statins to reduce the risk of a MACE, and aware that many other patients who are unable to tolerate a statin were actually able to tolerate a different statin or dose.

Note: Statin intolerance will be defined as intolerance due to an adverse safety effect that started or increased during statin therapy and resolved or improved when statin therapy was discontinued, resulting in an inability to tolerate either 1) two or more statins at any dose, or 2) one statin at any dose and either an unwillingness to attempt a second statin or advice by a physician not to attempt a second statin.²⁵

- o Bempedoic acid for at least 8 weeks in combination with a maximally tolerated statin prior to Screening (Visit 1); and/or
- A PCSK9-targeted therapy alone or in combination with other lipid-modifying therapy for at least 4 doses prior to Screening (Visit 1).

Note: Patients taking inclisiran must have received at least 2 stable doses prior to Screening.

Note: Approximately 70% of the participants enrolled into this study should be taking HIS. No more than approximately 10% of participants in this study will be completely statin intolerant. Documentation in the electronic case report form (eCRF) of the reason why a participant is unable to take HIS is required. HIS include atorvastatin 40 and 80 mg and rosuvastatin 20 and 40 mg.

5. Have a fasting serum LDL-C at Screening (Visit 1) \geq 70 mg/dL (\geq 1.8 mmol/L);

Note: For eligibility purposes, LDL-C at Screening (Visit 1) will be calculated using the Martin-Hopkins equation unless TG \geq 400 mg/dL (\geq 4.5 mmol/L) or LDL-C \leq 50 mg/dL (\leq 1.3 mmol/L); in both cases, LDL-C level will be measured directly by preparative ultracentrifugation, also referred to as beta quantification.²⁶

- 6. Have fasting TG <500 mg/dL (<5.7 mmol/L) at Screening (Visit 1); and
- 7. Have an estimated glomerular filtration rate (eGFR) ≥15 mL/min/1.73 m² calculated using the Chronic Kidney Disease Epidemiology Collaboration equation²⁷ at Screening (Visit 1).

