9.2 Statistical Methods

A Statistical Analysis Plan (SAP) will be finalized before database lock. Any changes to the methods described in the SAP will be described and justified as needed in the Clinical Study Report. All study-collected data will be summarized by treatment group using descriptive statistics, graphs, and/or raw data listings. Descriptive statistics for continuous variables will include number of participants (n), mean, standard deviation (SD), median, minimum, and maximum values. Analysis of categorical variables will include frequency and percentage.

Unless otherwise stated, baseline values will be the last non-missing measurements taken prior to the participant receiving any study drug.

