3.1.3 Definition of Baseline

Baseline is defined as the last measurement prior to the first dose of study drug, unless otherwise stated.

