- **Population level summary**: The difference in LS mean percentage change in LDL-C from Baseline to Day 84 between obicetrapib 10 mg + ezetimibe 10 mg FDC treatment versus placebo, ezetimibe 10 mg monotherapy, and obicetrapib 10 mg monotherapy, and obicetrapic 10 mg monotherapy versus placebo

The analysis of covariance (ANCOVA) model with a fixed effect for the treatment group and covariates of Baseline LDL-C will be used to analyze the primary efficacy endpoint. The least squares (LS) mean, standard errors, and 2-sided 95% confidence intervals for each treatment group and for the treatment comparison (FDC treatment – placebo, FDC treatment – ezetimibe 10 mg, and FDC treatment- obicetrapib 10 mg, and obicetrapib 10 mg - placebo) will be provided. Model diagnostics for the ANCOVA model will be computed that include assessment for homogeneity of variance, normality of the residual, and residual outliers. If substantial deviations from the model assumptions are observed, then supportive analyses, such non-parametric assessments, will be considered.

Missing data will be imputed for the primary efficacy analysis based on a pattern mixture model that uses a multiple imputation technique analyzed with ANCOVA with pre-specified fixed factors and covariates. If appropriate, based on the number of retrieved dropouts, missing measurements of non-retrieved dropouts will be modeled by known measurements from retrieved dropouts (i.e., participants who remain in the study after treatment discontinuation) in the same treatment group. If the number of retrieved dropouts is such that the model convergence is questionable and the given parameter estimates cannot be obtained, then missing data at the Day 84 assessment will be estimated based on the placebo treatment group as described in subsequent sections of the SAP corresponding to the first sensitivity analysis.

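### The efficacy ANCOVAs adjust for one Day 1 lipid value and leave out the fasting Screening value already collected; adding it as a second covariate would give a small, free gain in precision

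*SAP*

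**What the plan says.** **Endpoint and baseline.** SAP 2.3.1: "The primary efficacy endpoint is the percent change from Day 1 to Day 84 in LDL-C". The secondary endpoints in SAP 2.3.2 are also percent changes from Day 1. SAP 3.1.3: "Baseline is defined as the last measurement prior to the first dose of study drug, unless otherwise stated". Protocol 9.2 says nearly the same: "baseline values will be the last non-missing measurements taken prior to the participant receiving any study drug".

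**Model.** SAP 3.4.1 uses an ANCOVA "with a fixed effect for the treatment group and covariates of Baseline LDL-C will be used to analyze the primary efficacy endpoint". SAP 3.4.2 applies similar models to non-HDL-C and ApoB.

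**What is collected.** In SAP Table 1 the row "Fasting lipid profile" is marked at Screening and at Visit 2 (Day 1). The two visits are at most two weeks apart (SAP 2.2.1). Protocol Appendix B lists LDL-C, non-HDL-C and ApoB in that profile. Screening LDL-C of at least 70 mg/dL is an entry criterion (Protocol 4.1, criterion 5), so eligible participants should have a value.

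**Method.** The primary analysis uses LDL-C by preparative ultracentrifugation only (SAP 3.4.1). Everyone has this at Day 1 and Day 84, but not at Screening. Screening LDL-C comes from the Martin-Hopkins equation, except at high triglycerides or low LDL-C (Protocol 4.1).

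**The concern.** A single lipid reading carries day-to-day variation. If Day 1 happens to read high, the percent change looks too favourable, and the reverse if it reads low. Adjusting for the Day 1 value removes part of this, but one noisy reading cannot show how far it lies from the participant's usual level. A second reading before randomisation supplies some of that information.

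What is at stake is the width of the confidence intervals for the four co-primary and eight secondary contrasts. FDC against obicetrapib has the least room. All four co-primary tests must succeed before any secondary is tested, so that contrast is where added precision would count most.

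**Working it through.** **Inputs from the documents (SAP 2.2.2).** 95 evaluable participants per arm, SD 25, one-sided 0.025, and differences of 30, 20, 15 and 12 points. Dropout is about 5%, with 400 enrolled.

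**Assumed, because the documents are silent.** Within-person SD on the log scale (w) 0.05 to 0.15. Between-person log SD (b) 0.25, with 0.30 as a check. Extra disagreement between Martin-Hopkins and ultracentrifugation (m) 0.05. SD 25 is taken as the residual SD given Day 1; the SAP does not say whether it is raw or residual.

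**Step 1: the plan's own power.** The standard error of a difference is 25 × √(2/95) = 3.627. For 12 points, 12/3.627 = 3.308, and Φ(3.308 − 1.960) = 0.911; the noncentral t with 188 df gives 0.908. The same normal formula gives 0.985 for 15 points, 0.9998 for 20 and above 0.999 for 30. Enrolment is 95/0.95 = 100 per arm. Every stated figure reproduces.

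**Step 2: what a second reading removes.** The variance of a participant's true log level, given the readings, is:

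- Day 1 alone: V1 = 1/(1/b² + 1/w²)
- Day 1 and Screening: V2 = 1/(1/b² + 1/w² + 1/(w² + m²))

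As a share of the residual variance (0.25² = 0.0625), the cut is (V1 − V2)/0.0625. That applies when LDL-C does not fall. With a 30% fall, baseline error enters the percent change multiplied by 0.7, so the cut is multiplied by 0.49.

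Example, w = 0.10 and b = 0.25: V1 = 1/(16 + 100) = 0.00862. V2 = 1/(16 + 100 + 80) = 0.00510. The cut is 0.00352/0.0625 = 5.6% with no fall, and 5.6 × 0.49 = 2.8% with a 30% fall.

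**Step 3: simulation check.** Screening, Day 1 and Day 84 values were simulated around a median of 100 mg/dL. Screening was truncated at 70 mg/dL, and response variation was tuned so that the residual SD given Day 1 was 25. The simulation column covers b of 0.25 and 0.30. Power uses the noncentral t.

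| w | Cut by formula, 30% fall | Cut by simulation, 30% fall | Residual SD | Power for 12 points |
|---|---|---|---|---|
| 0.05 | 0.6% | 0.6% | 24.9 | 0.910 |
| 0.08 | 1.8% | 1.5–1.6% | 24.8 | 0.913 |
| 0.10 | 2.8% | 2.4% | 24.7 | 0.915 |
| 0.15 | 5.2% | 4.2–4.7% | 24.4–24.5 | 0.919–0.921 |

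Rounded, this is a cut of 0.5 to 5%. In sample-size terms that is 400 × 0.005/0.995 ≈ 2 to 400 × 0.05/0.95 ≈ 21 participants. With no fall in LDL-C the simulated cut is about 1 to 10%.

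**Step 4: non-HDL-C and ApoB.** These have no LDL-C method switch, so m = 0. With the other assumptions unchanged, the simulated cut is about 0.9 to 5.1% at a 30% fall. The documents give no SD for these analytes, so this is only a guide.

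**Step 5: the imputation model.** SAP 3.4.1 fits the retrieved-dropout model only to participants who stopped treatment or lack a Day 84 value. Its coefficients therefore come from retrieved dropouts alone. Planned dropout is 5% of 400, about 20 in all, and the number retrieved is not given. In simulations of out-of-sample prediction of Day 84 LDL-C, adding Screening raised mean squared error by roughly 11 to 18% with 12 retrieved dropouts. With 20, the result ranged from no change to about 6% worse.

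**The case against.** The strongest reply is that nothing is broken. The Day 1 baseline is used consistently, ANCOVA on it is valid, and the main part of the mechanism is already handled because the model adjusts for Day 1. The gain is a fraction of a power point to a little over one, and it rests on variation that the documents do not report. If SD 25 is a raw figure, power already exceeds 0.91. All of this stands, and it sets the priority.

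It is also fair that Screening is not a clean replicate. It uses another LDL-C method, is selected at 70 mg/dL, may follow only a 14-day gap off ezetimibe (Protocol 4.2), and may be retested or come from rescreening (Protocol 4.3 and 4.4). These points limit the gain and call for explicit rules. They do not bias a covariate measured before randomisation.

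A reader might infer more than the documents support:

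- **That the contrasts are biased or the power statement is wrong.** Randomisation protects the contrasts, and each stated power figure reproduces.
- **That the baseline should be the mean of Screening and Day 1.** The primary endpoint is ultracentrifugation LDL-C, which has no routine Screening value. Averaging would mix methods in the denominator and change the endpoint.
- **That Screening values are never used.** The last-measurement rule lets Screening stand in as baseline when Day 1 is missing, for example for ApoB.
- **That the same value would sharpen the imputation.** Step 5 points the other way when retrieved dropouts are few.

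**Conclusion.** The point holds as an efficiency remark. The plan adjusts for one pre-dose lipid value when two are in hand, and so gives up a small amount of precision. For the tightest LDL-C contrast the loss is roughly 0.5 to 5% of residual variance, or power for 12 points of about 0.91 against 0.91 to 0.92. The gain may be somewhat larger for non-HDL-C and ApoB. These sizes depend on an assumed within-person variation of 5 to 15%, an assumed 5% method disagreement, and on reading SD 25 as residual. There is no bias, no wrong figure and no threat to the trial's conclusions. Label: free improvement, low priority.

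**What to change.** Keep percent change from Day 1 as the endpoint and the Day 1 value as a covariate. Before unblinding:

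1. In the SAP 3.4.1 ANCOVA, add Screening LDL-C as a second continuous covariate. In SAP 3.4.2, add the Screening value of non-HDL-C or ApoB to the model for that analyte.
2. State that the last valid Screening value before Day 1 is used. This covers retests and rescreening.
3. State a simple treatment-blind fill, such as the mean over all randomised participants, for a Screening value that is missing or that already serves as the baseline. Without it, a missing Screening ApoB or non-HDL-C would drop the participant, because SAP 3.1.7 allows no imputation for secondary endpoints.
4. Leave the retrieved-dropout imputation model as it is.
5. List the change in SAP Section 5, since Protocol 9.2.1.1 names a single covariate.

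The cost is a few sentences, one term in the code and one degree of freedom per model. No new samples or visits are needed.
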